#### Table KGBO.5.3. Seed Values for MCMC-Multiple Imputation

Abbreviations: CDLQI = Children's Dermatology Life Quality Index; DLQI = Dermatology Life Quality Index ; EASI = Eczema Area and Severity Index; EASI-75 = Eczema Area and Severity Index improvement of  $\geq$ 75%; EASI-90 = Eczema Area and Severity Index improvement of  $\geq$ 90%; IGA = Investigator's Global Assessment for Atopic Dermatitis; LEB = lebrikizumab; MCMC = Markov chain Monte Carlo; NRS = Numeric Rating Scale; Q2W = every 2 weeks; Q4W = every 4 weeks; SCORAD = SCORing Atopic Dermatitis.

#### 5.5. Multicenter Studies

This study will be conducted by multiple investigators at multiple sites.

### 5.6. Multiple Comparisons/Multiplicity

No statistical tests will be performed in this study so there is no need to account for multiple comparisons.

## 5.7. Patient Disposition

The following patient disposition summaries will be provided (details of the analysis populations can be found in Section 5.1.1):

- The total number and percentage of patients entering each statistical analysis population as defined in Section 5.1.1 (analysis population: all entered patients).
- The number and percentage of patients who entered the study, were treated, and screen failed will be provided overall and by screen fail reason (analysis population: all entered patients).
- The number and percentage of patients who completed Week 16, and the number and percentage of patients who discontinued the treatment at any time before Week 16, by primary reason for discontinuation of treatment (analysis population: ITT).
- The number and percentage of patients who completed Week 24, and the number and percentage of patients who discontinued the treatment at any time before Week 24, by primary reason for discontinuation of treatment (analysis population: ITT).
- The number and percentage of patients who were treated and completed the study, and the number and percentage of patients who discontinued the study at any time, by primary reason for discontinuation (analysis population: ITT).

All enrolled participants (that is, in the ITT population) who discontinued from study treatment will be listed together with the discontinuation reason, and the timing of discontinuation from the study will be reported.

Patient allocation by center/site will be summarized with the number of patients who entered the study, number of ITT patients, number of patients discontinued from study treatment, and number of patients discontinued from the study.

# 5.8. Patient Characteristics

## 5.8.1. Demographics and Baseline Characteristics

Patient demographic variables and baseline characteristics will be summarized for the ITT and Treatment Period II populations. The continuous variables will be summarized using descriptive statistics (mean, median, standard deviation, and range [minimum and maximum]), and the categorical variables will be summarized using frequency counts and percentages.

The following demographic information will be included:

- age
- sex (male, female)
- reason of prior dupilumab discontinued
- Fitzpatrick skin phototype
- race (American Indian or Alaska Native, Asian, Black or African American, Native Hawaiian or Other Pacific Islander, White, Multiple, Other, or Not Reported)
- ethnicity (Hispanic or Latino, Not Hispanic or Latino, Not reported, or Unknown)
- weight (kg)
- weight category (40- $\leq$ 60 kg,  $\geq$ 60 to  $\leq$ 100 kg, or  $\geq$ 100 kg)
- height (cm)
- BMI (kg/m^2), and
- BMI category (Underweight [<18.5 kg/m^2], Normal [≥18.5 and <25 kg/m^2], Overweight [≥25 and <30 kg/m^2], Obese [≥30 and <40 kg/m^2], or Extreme obese [≥40 kg/m^2]).

By-patient listings of basic demographic information for the ITT population will be provided.

The following baseline disease/clinical characteristics will be included:

- age at onset (years): calculated as the difference between date of onset of AD and the date of birth collected on the CRF
- duration since AD onset (years): calculated as the difference between date of informed consent and the date of onset of AD collected on the CRF
- duration since AD onset category (0 to <2 years, 2 to <5 years, 5 to <10 years, or ≥10 years)

- anatomical area affected by AD:
  - o head
  - trunk (internal/medial axillae and groin)
  - upper extremities (includes external axillae)
  - o lower extremities (includes buttocks and feet), and
  - o at least 2 areas
- AD treatment used in the past:
  - o none
  - topical corticosteroids
  - o topical calcineurin inhibitors

immunosuppressive/immunomodulating drugs: systemic corticosteroids, cyclosporine, mycophenolate-mofetil, IFN-γ, janus kinase inhibitors, azathioprine, methotrexate, phototherapy, photochemotherapy, and other biologics (eg, B-cell depleting biologics)

The following efficacy instruments will be included:

- IGA
- F-IGA score
- EASI score
- BSA
- SCORAD
- mTLSS
- Pruritus NRS
- Sleep-Loss Scale
- Skin Pain NRS
- DLQI/CDLQI
- ADCT
- Participant-Reported Satisfaction Question
- Fitzpatrick Skin Phototype Assessment
- WPAI-AD.

#### 5.8.2. Medical History

Medical histories are defined as the conditions/events recorded on the *Pre-existing Conditions and Medical History* eCRF with a start date prior to the first study drug injection. Notice if a medical history worsens in severity on or after the date of first injection it will be recorded as an AE on the *Adverse Event* eCRF with the date of worsening as the start date.

The number and percentage of patients with medical histories will be summarized for the ITT population using the MedDRA Preferred Term (PT) nested within System Organ Class (SOC).

The number and percentage of patients with specific medical history events of interest prespecified on the *Prespecified Medical History* eCRF will be summarized for the ITT population.

#### 5.9. Treatment Compliance

Beginning Week 4 (Visit 4) the participant/caregiver will be encouraged to administer the study intervention while in the clinic or at home. Participants may choose to continue to receive study drug injections administered by trained clinic staff for any visit occurring in the clinic. Home

dosing must be self-administered or given by a caregiver that has received proper injection technique training.

When participants self-administer study intervention(s) at home, compliance with study intervention will be assessed at each visit. Compliance will be assessed by direct questioning, counting returned injection supplies, and documented in the source documents.

Treatment compliance with investigational product will be summarized for patients who receive at least 1 confirmed dose of lebrikizumab (ie, the Safety Population) during the Treatment Period. Treatment compliance for each patient will be calculated as:

 $Treatment \ compliance \ (\%) = 100 \times \frac{Total \ number \ of \ injections \ administered}{Total \ number \ of \ injections \ expected}$ 

- The number of injections expected can be derived from the study drug dispense dataset.
- The total number of injections administered will be based on the *Exposure as Collected* eCRF page and on the *Exposure as Collected: Missed Injections at Home* eCRF page.

A patient will be considered compliant if he or she received  $\geq$ 75% of the expected number of injections while enrolled in the study. Descriptive statistics for percent compliance will be summarized. Subintervals of interest, such as compliance between visits, may also be presented.

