Week Relative to Study Drug Start	≤30 (days)	0	2	4	8	12	16	20	24	-	Approximately 12 weeks post last dose	
Visit Interval Tolerance (Days)		-	±3	±3	±5	±5	±5	±5	±5	-	±7	
Visit Detail						T		T				
Registration and Dosing												
Register visit with IWRS	X	X	X	X	X	X	X	X	X	X	X	
Dispense study intervention via IWRS		X	X	X	X		X					
Administer study intervention in clinic		X	X	X	X		X					Week 0 (Visit 2) and Week 2, dose to be administered in the clinic by site. Weeks 4, 8, and 16 dosing to be performed in clinic administered by site or participant or caregiver.
Dispense study intervention to participant for at home dosing				X	X		X					Injections will be administered by participant or caregiver at home on Weeks 6, 10, 12, and 14. Responders at Week 16 who will receive Q4W dose will administer study intervention at Week 20. Inadequate responders at Week 16 who will receive Q2W dosing will administer study intervention at Weeks 18, 20, and 22.
Observe participant or caregiver administer study intervention				X								

	Period I	Period II									Period III	Comments
	Screening	Baseline	Treatment Period									
Visit Number	1	2	3	4	5	6	7	8	9	ED	801	
Week Relative to Study Drug Start	≤30 (days)	0	2	4	8	12	16	20	24	-	Approximately 12 weeks post last dose	
Visit Interval Tolerance (Days)		-	±3	±3	±5	±5	±5	±5	±5	-	±7	
Visit Detail						T		T				
Participant returns study intervention					X		X		X	X		If study intervention was administered at home by participant or caregiver, the injection supplies should be saved and returned at the next on-site visit.
Assess study intervention compliance					X		X		X			

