6.1. Study Intervention(s) Administered

Lebrikizumab drug product is provided as sterile liquids and contain no preservatives.

Intervention Name	Lebrikizumab
Dose Formulation	250 mg (125 mg/mL), 2 mL Solution
Dosage Level	
Loading Dose:
 
Week 0: 500 mg (2 injections of 250 mg) Week 2: 500 mg (2 injections of 250 mg)
 
Post-loading Dose:
 
Weeks 4-16: 250 mg SC Q2W (1 injection of 250 mg) Responders at Week 16: 250 mg SC Q4W (1 injection of 250 mg) at W20 Inadequate responders at Week 16: 250 mg SC Q2W (1 injection of 250 mg) at W18, W20, and W22

Route of Administration	SC

Abbreviations: mg = milligram; mL = milliliter; SC = subcutaneously; Q2W = every 2 weeks; Q4W = once every 4 weeks; W = week.

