## 5.15. Protocol Deviations

Protocol deviations will be identified throughout the study. Important protocol deviations are defined as those deviations from the protocol likely to have a significant impact on the completeness, accuracy, and/or reliability of the study data or that may significantly affect a patient's rights, safety, or well-being.

Potential examples of important protocol deviations include patients who violated the inclusion/exclusion criteria, used an interfering concomitant medication, and significant non-compliance with study medication (<75% of expected injections). Refer to a separate document called "KGBO Trial Issues Management Plan" for the important protocol deviations with categorizations.

The number and percentage of patients having important protocol deviations will be summarized within category and subcategory of deviation for Weeks 0-16 of the Treatment Period using the ITT population and for Weeks 16-24 of the Treatment Period using the Treatment Period II Population.

A by-patient listing of important protocol deviations will be provided for the ITT population.

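### Taking expected injections from dispensing records lets never-dispensed doses drop out of the compliance ratio, so a missed Week 8 visit can read as 100% compliance

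*SAP*

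**What the plan says.** SAP Section 5.9 defines treatment compliance as 100 times injections administered divided by injections expected, summarised for the Safety Population over the Treatment Period.

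- **Denominator:** "The number of injections expected can be derived from the study drug dispense dataset". The section gives no dosing schedule, no time window and no rule for a missed dispensing visit.
- **Numerator:** "The total number of injections administered will be based on the" two exposure eCRF pages, one of which records injections missed at home.
- **Threshold:** a participant is compliant at 75% or more "of the expected number of injections while enrolled in the study".

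SAP Section 5.15 lists, among possible examples of important protocol deviations, "significant non-compliance with study medication (<75% of expected injections"), and refers to a separate issues management plan for the actual categories.

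Protocol Section 6.1 fixes the number of injections. The loading doses are "Week 0: 500 mg (2 injections of 250 mg) Week 2: 500 mg (2 injections of 250 mg"), followed by "Weeks 4-16: 250 mg SC Q2W (1 injection of 250 mg"). After Week 16, responders receive "250 mg SC Q4W (1 injection of 250 mg) at W20", and inadequate responders receive one injection at each of Weeks 18, 20 and 22. The Schedule of Activities (Protocol Section 1.3) dispenses drug at Weeks 0, 2, 4, 8 and 16 only. Week 12 is a telephone visit. The doses at Weeks 4, 8 and 16 are taken in clinic, and "Injections will be administered by participant or caregiver at home on Weeks 6, 10, 12, and 14".

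**The concern.** A compliance ratio should compare what was taken with what the protocol called for. A dispensing count measures what was handed out. The two agree only when every dispensing visit takes place. When one does not, the doses it would have supplied disappear from both parts of the ratio, and the participant appears fully compliant with a regimen that was not received.

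This design is sensitive to the problem because dispensing is uneven: one visit, Week 8, supplies all treatment until Week 16, where the primary endpoint is measured. The compliance summary is the one planned table that sets injections received against an expected number. The less-than-75% example in Section 5.15 would inherit the error if it uses the same denominator.

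**Working it through.** The documents state no total of expected injections to reproduce, so the schedule is counted directly.

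**Scheduled injections (Protocol Section 6.1)**

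- Weeks 0 and 2: 2 + 2 = 4.
- Weeks 4, 6, 8, 10, 12, 14 and 16: 7.
- Total to Week 16: 4 + 7 = 11.
- Total to Week 24, Q4W: 11 + 1 = 12.
- Total to Week 24, Q2W: 11 + 3 = 14.

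**Injections supplied at each dispensing visit.** The Schedule of Activities does not state quantities, so each dose is assigned to the latest dispensing visit at or before it.

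- Week 0: 2.
- Week 2: 2.
- Week 4: 2 (Weeks 4 and 6).
- Week 8: 4 (Weeks 8, 10, 12 and 14).
- Week 16: 1 for that day, plus 1 (Q4W) or 3 (Q2W) for home use.

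Check to Week 16: 2 + 2 + 2 + 4 + 1 = 11.

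**Week 8 visit missed, all other doses dispensed and taken**

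Dispense-based compliance = administered / dispensed. Schedule-based compliance = administered / scheduled.

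| Window | Scheduled | Dispensed | Administered | Dispense-based | Schedule-based |
|---|---|---|---|---|---|
| To Week 16 | 11 | 11 − 4 = 7 | 7 | 7/7 = 100% | 7/11 = 63.6% |
| To Week 24, Q4W | 12 | 12 − 4 = 8 | 8 | 8/8 = 100% | 8/12 = 66.7% |
| To Week 24, Q2W | 14 | 14 − 4 = 10 | 10 | 10/10 = 100% | 10/14 = 71.4% |

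All three schedule-based figures are below 75%, so the participant is classed as compliant on one denominator and non-compliant on the other.

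**Other single missed visits**

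- Week 2 or Week 4 (2 injections lost): 9/11 = 81.8% to Week 16; 10/12 = 83.3% or 12/14 = 85.7% to Week 24. The ratio is still overstated at 100%, but the classification does not change.
- Week 16: 10/12 = 83.3% on Q4W or 10/14 = 71.4% on Q2W. This case is less clear, because the later regimen is assigned from the Week 16 assessment.

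**Whether other parts of Section 5.9 repair the ratio**

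- The page for injections missed at home feeds the numerator only. It does not put undispensed doses back into the denominator.
- The section allows compliance between visits to be presented. On the same denominator, the interval supplied by Week 8 would be 0 administered over 0 dispensed, which is undefined rather than low.

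**The case against.** The strongest case on the other side is that this is a descriptive table with little resting on it, and that the scenario is narrow.

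- **The wording is permissive.** The SAP says the expected number can be derived from dispensing data and does not define the count as syringes handed out. This stands as a condition on the result. But no other source or rule is given, so a programmer following the text would use the dispensing count.
- **The scenario needs several things together.** Week 8 must be missed outright, with no late dispensing, and the participant must return and be fully dosed otherwise. The documents give no basis for a frequency. This also stands.
- **The size depends on visit and window.** A reader might infer that any missed dispensing visit conceals more than a third of the injections. Only Week 8 does, and only to Week 16 (4/11 = 36.4%). Over 24 weeks the loss is 4/12 = 33.3% or 4/14 = 28.6%.
- **The shortfall is not hidden everywhere.** A reader might infer that the planned outputs would conceal these participants. They would not: SAP Section 5.13.1 lists injections and total dose by participant, from the exposure pages rather than from dispensing. A total of 8 or 10 injections would show there, though not set against the schedule.
- **No efficacy result changes.** A reader might infer that the primary analysis is compromised. Compliance defines no analysis population in SAP Section 5.1.1 and enters no estimand in Section 5.2. The primary estimand conditions on remaining on study treatment, not on a compliance cut.
- **The deviation flag is not shown to be wrong.** Section 5.15 gives less than 75% only as a possible example and defers to a plan that is not among the documents.
- **A bare schedule count has its own fault.** Protocol Sections 7.1.1 and 7.1.2 provide for interrupting or withholding drug. Counting those doses as missed would label adherence to the protocol as non-compliance. This is correct, and the fix has to deal with it.

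**Conclusion.** The point holds as a defect in the compliance measure. With expected injections taken from dispensing, one missed Week 8 visit gives a reported 100% where the schedule gives 63.6% to Week 16, and 66.7% (Q4W) or 71.4% (Q2W) to Week 24, all below the SAP's own threshold. This rests on three assumptions: the dataset counts syringes actually dispensed, no make-up dispensing takes place, and the Week 8 visit supplies the doses through Week 14. The last is inferred from the visit schedule. How often it would happen is unknown.

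The consequence is limited to the compliance summary and, if the same denominator is used there, the less-than-75% example in Section 5.15. It is worth correcting because the stated rule misclassifies the participants the table exists to identify, and the correction needs no new data.

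**What to change.** 1. In SAP Section 5.9, define expected injections from the Schedule of Activities, from first dose to the earlier of the end of the treatment period or permanent treatment discontinuation, using the Q2W or Q4W schedule assigned at Week 16.
2. State how doses withheld under Protocol Sections 7.1.1 and 7.1.2 are counted, for example by leaving them out of the denominator or tabulating them separately, so that they are not labelled non-compliance.
3. Use the dispensing dataset for reconciliation only.
4. Use the same denominator for the less-than-75% criterion in Section 5.15.

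The cost is revised SAP wording and one extra derivation. Reported compliance may be slightly lower.

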## 5.10. Prior and Concomitant Therapy

Medications will be classified into anatomical therapeutic chemical (ATC) drug classes using the latest version of the World Health Organization (WHO) drug dictionary. Medication start and stop dates will be compared to the date of first dose of treatment during Weeks 0-16 of the Treatment Period and Weeks 16-24 of the Treatment Period to be classified as concomitant for each treatment period.

*Prior medications* are those medications that start and stop prior to the date of first dose of study treatment. *Concomitant medications* are those medications that start before, on, or after the first day of study treatment of the defined study period (that is, Weeks 0-16 or Weeks 16-24 of the Treatment Period) and continue into that period. Concomitant medications are assigned to the study period in which they are actually ongoing. For example, if a participant is receiving a concomitant medication during Weeks 0-16 but has a stop date prior to Week 16, the same medication would not be listed as a concomitant medication for Weeks 16-24 unless the patient has a new start date.

Prior medication will be summarized by drug class and PT for the ITT population. Concomitant medication used during Weeks 0-16 and Weeks 16-24 will be presented separately for the ITT and Treatment Period II populations.

Rescue medications used during Weeks 0-16 and Weeks 16-24 will be presented separately for the ITT and Treatment Period II populations. This will include: (1) topical therapy and (2) systemic therapy (e.g., systemic corticosteroids, phototherapy, cyclosporin, etc.). More information on the definition of rescue medications can be found in Appendix 1.

## 5.11. Efficacy Analyses

Table KGBO.5.4 includes the description and derivation of the efficacy measures and endpoints.

For categorical parameters, the number and percentage of patients in each category will be presented, as well as a 90% Wilson-Score confidence interval for the percentage. For continuous parameters, descriptive statistics will include n (number of patients), mean, standard deviation, Q1, median, Q3, minimum, and maximum. These summaries will be provided for the data asobserved and after implementation of LOCF and MCMC-MI imputation as described in Sections 5.4.2 and 5.4.3.

The IGA, F-IGA, EASI, BSA, Pruritus NRS, Skin Pain NRS, and Sleep-Loss Scale will be reported by clinic visit.

#### Table KGBO.5.4.Description and Derivation of Efficacy/Health Outcomes Measures and Endpoints

Measure	Description	Variable	Derivation/Comment	Imputation Approach if Missing Components
Investigator's Global Assessment	The IGA is a static assessment and rates the severity of a patient's AD. The IGA is comprised of a 5-point scale ranging	IGA score	Single item. Range: 0-4 0 represents "clear" 4 represents "severe"	Single item, missing if missing
(IGA)	from 0 (clear) to 4 (severe), and a score is selected using descriptors that best describe the overall appearance of the lesions at a given time point.	
 
IGA (0,1) with ≥2-point improvementa IGA (0)
 
	
 
Observed score of 0 or 1 and change from baseline ≤-2
 
Observed score of 0
 
	Missing if baseline or observed value is missing Single item, missing if
Face- Investigator's Global Assessment (F-IGA)	The F-IGA is a static assessment and rates the severity of a patient's AD on the face. The F-IGA is comprised of a 5-point scale ranging from 0 (clear) to 4 (severe), and a score is selected using descriptors that best describe the overall appearance of the lesions at a given time point.	F-IGA Score IGA (0,1) with ≥2-point improvement a IGA (0)	Single item. Range: 0-4, 0 represents "clear", 4 represents "severe" Observed score of 0 or 1 and change from baseline ≤-2 Observed score of 0	missing Single item, missing if missing Missing if baseline or observed value is missing Single item, missing if missing
Eczema Area and Severity Index (EASI)	The EASI scoring system uses a defined process (Steps 1-5 below) to grade the severity of the signs of eczema and the extent affected. The extent of disease (percentage of skin affected: $0 = 0\%$ ; 1 = 1-9%; $2 = 10-29%$ ; $3 = 30-49%$ ; 4 = 50-69%; $5 = 70-89%$ ; $6 = 90-100%$ ) and the severity of 4 clinical signs (erythema, edema/papulation, excoriation, and lichenification) each on a scale of 0-3 ( $0 =$ none, absent; 1 = mild; $2 =$ moderate; $3 =$ severe) at 4	EASI score	Derive EASI region score for each of head and neck, trunk, upper limbs, and lower limbs as follows: EASI region = (erythema + edema/papulation + excoriation + lichenification)*(value from percentage involvement), where erythema, edema/papulation, excoriation, and lichenification are evaluated on a scale of 0 to 3, and value from percentage involvement is on a scale of 0 to 6. Then total EASI score is as follows:	NA: partial assessments cannot be saved.

	body sites (head and neck, trunk, upper limbs, and lower limbs). Half scores are allowed between severities 1, 2, and 3.		$\begin{split} EASI &= 0.1*EASI_{head and neck} + \\ 0.3*EASI_{trunk} + 0.2*EASI_{upper limbs} + \\ 0.4*EASI_{lower limbs} \end{split}$	
	Each body site will have a score that ranges from 0-72, and the final EASI score will be obtained by weight- averaging these 4 scores. Hence, the	Change from     baseline in EASI     score	Change from baseline: observed EASI score – baseline EASI score	Missing if baseline or observed value is missing
	final EASI score will range from 0-72 for each time point.	Percent change from baseline EASI score a	% change from baseline: 100 × Baseline	
		EASI-75ª	% improvement in EASI score from baseline ≥75%: % change from baseline ≤-75	Missing if baseline or observed value is missing
		EASI-90ª	% improvement in EASI score from baseline ≥90%: % change from baseline ≤-90	Missing if baseline or observed value is missing
Body Surface Area (BSA) Affected by	The BSA assessment estimates the extent of disease or skin involvement with respect to AD and is expressed as a	BSA score	$\begin{split} BSA \ Total &= BSA_{head} \ and \ neck + \\ BSA_{trunk} + BSA_{upper} \ limbs + BSA_{lower} \\ limbs \end{split}$	NA: partial assessments cannot be saved.
AD	percentage of total body surface. BSA will be determined by the investigator or designee using the patient palm = $1\%$ rule.	Change from baseline in BSA score a	Change from baseline: observed BSA score - baseline BSA score	Missing if baseline or observed value is missing.
Dermatology Life Quality Index (DLQI)	The DLQI is a validated, dermatology- specific, patient-reported measure that evaluates a patient's HRQoL. This questionnaire has 10 items that are grouped in 6 domains, including symptoms and feelings, daily activities, leisure, work and school, personal relationships, and treatment. The recall	DLQI total score	A DLQI total score is calculated by summing all 10 question responses and has a range of 0-30 (less to more impairment) (Finlay and Khan 1994; Basra et al. 2008).	Score of 1 unanswered question = 0; If 2 or more questions are missing, the total score is missing. Note: #7B could be a valid missing while #7A is not "No." That is, #7 should be considered as 1 question.
	period of this scale is over the "last week".	DLQI (0,1)	A DLQI (0,1) response is defined as a postbaseline DLQI total score of 0 or 1. A DLQI total score of 0-1 is considered as having no effect on a patient's	Missing if DLQI total score is missing

Response categories and corresponding		HRQoL (Khilji et al. 2002; Hongbo et	
scores are: Very much = 3	4-point improvement a	al. 2005). Change from baseline ≤-4	Missing if baseline is
A lot = $2$	+ point improvement		missing or observed value is
A little = $1$			missing.
Not at all $= 0$	DLQI total score and	Calculated as: observed DLQI (total	Missing if baseline or
Not relevant $= 0$	domain scores change	score or domain scores) - baseline	observed value is missing
	from baseline a	DLQI (total score or domain scores)	C
Scores range from 0-30, with higher			
scores indicating greater impairment of			
QoL. A DLQI total score of 0-1 is			
considered as having no effect on a			
patient's HRQoL (Hongbo et al. 2005),			
and a 4-point change from baseline is			
considered as the minimal clinically			
important difference threshold (Khilji et			
al. 2002; Basra et al. 2015).			
	DLQI symptoms and	Sum of responses of questions 1 and 2:	If 1 question in a domain is
	feelings domain	1. How itchy, sore, painful or stinging	missing, that domain is
		has your skin been?	missing.
		2. How embarrassed or self-conscious	
		have you been because of your	
		skin?	
	DLQI daily activities	Sum of responses of questions 3 and 4:	If 1 question in a domain is
	domain	3. How much has your skin interfered	missing, that domain is
		with you going shopping or looking	missing.
		after your home or garden?	
		4. How much has your skin influenced	
	DLOIL :	the clothes you wear?	TC 1
	DLQI leisure domain	Sum of responses of questions 5 and 6: 5. How much has your skin affected any	If 1 question in a domain is
		5. How much has your skin affected any	missing, that domain is

			social or leisure activities? 6. How much has your skin make it difficult for you to do any sport?	missing.
		DLQI work and school domain	
 
Sum of responses of questions 7A and 7B:
 
7A. Has your skin prevented you from working or studying?
 
7B. If No: how much has your skin been a problem at work or studying?
 
	If the answer to question 7A is missing, this domain is missing. If 7A is No, and 7B is missing, this domain is missing.
		DLQI personal relationships domain	
 
Sum of responses of questions 8 and 9:
 
8. How much has your skin created problems with your partner or any of your close friends or relatives?
 
9. How much has your skin caused any sexual difficulties?
 
	If 1 question in a domain is missing, that domain is missing.
		DLQI treatment domain	Response of question 10: 10. How much of a problem has the treatment for your skin been, for example by making your home messy, or by taking up time?	If 1 question in a domain is missing, that domain is missing.
Dermatology Life Quality Index (CDLQI) impact of any of children. F complete the continue to c duration of th The scoring of • Very mut	The CDLQI is designed to measure the impact of any skin disease on the lives of children. Patients ≤16 years will complete the CDLQI and should	CDLQI total score	A CDLQI total score is calculated by summing all 10 question responses and has a range of 0-30 (less to more impairment) (Waters A et al. 2010).	Score of 1 unanswered question = 0; If 2 or more questions are missing, the total score is missing.
	
 
continue to complete the CDLQI for the duration of the study.
 
The scoring of each question is:
 
Very much = 3
 
Quite a lot = 2
 
	CDLQI (0,1)	A CDLQI (0,1) response is defined as a postbaseline CDLQI total score of 0 or 1.	Missing if CLQI total score is missing
		4-point improvement a	Change from baseline ≤-4	Missing if baseline or observed value is missing
	
 
Quite a lot - 2
 
Only a little = 1
 
Not at all = 0
 
Question unanswered = 0
 
	CDLQI total score and domain scores change from baseline a	Calculated as: observed CDLQI (total score or domain scores) - baseline CDLQI (total score or domain scores)	Missing if baseline or observed value is missing
		CDLQI symptoms and feelings domain	Sum of responses of questions 1 and 2: 1. Over the last week, how itchy,	If 1 question in a domain is missing, that domain is

• Question 7: 'Prevented school' (text-only questionnaire) = 3		
 
"scratchy", sore or painful has your skin been?
 
2. Over the last week, how embarrassed or self conscious, upset or sad have you been because of your skin?
 
	missing.
	CDLQI sleep domain	Response of question 9 9. Over the last week, how much has your sleep been affected by your skin problem?	Single item, missing if missing
	CDLQI leisure domain	
 
Sum of responses of questions 4, 5, and 6:
 
4. Over the last week, how much have you changed or worn different or special clothes/shoes because of your skin?
 
5. Over the last week, how much has your skin trouble affected going out, playing, or doing hobbies?
 
6. Over the last week, how much have you avoided swimming or other sports because of your skin trouble?
 
	If 1 question in a domain is missing, that domain is missing.
	CDLQI school or holiday domain	Responses of questions 7: If select 'Prevented school', score = 3	Single item, missing if missing

Page 3	36
--------	----

			Last week, was it school time?If school time: Over the last week, how much did your skin affect your school work?ORSchool work?Was it holiday time?If holiday time: How much over the last week, has your skin problem interfered with your enjoyment of the holiday?	
		CDLQI personal relationships domain	
 
Sum of responses of questions 3 and 8:
 
3. Over the last week, how much has your skin affected your friendships?
 
8. Over the last week, how much trouble have you had because of your skin with other people calling you names, teasing, bullying, asking questions or avoiding you?
 
	
		CDLQI treatment domain	Response of question 10: 10. How much of a problem has the treatment for your skin been?	Single item, missing if missing.
SCORing Atopic Dermatitis (SCORAD)	
 
SCORAD is a validated clinical tool for assessing the extent and intensity of atopic dermatitis. There are 3 components to the assessment:
 
The extent of AD is assessed as a percentage of each
 
	SCORAD Score	SCORAD = $A/5 + 7B/2 + C$ , where A is extent of disease, range 0-100 B is disease severity, range 0-18 C is subjective symptoms, range 0-20	Missing if components A and B are missing or if component C is missing. Partial assessments performed by physician cannot be saved and partial

	
 
defined body area and reported as the sum of all areas, with a maximum score of 100% (assigned as "A" in the overall SCORAD calculation).
 
The severity of 6 specific symptoms of AD (redness, swelling, oozing/crusting, excoriation, skin thickening/lichenification, dryness) is assessed using the following scale: none (0), mild (1), moderate (2), or severe (3) (for a maximum of 18 total points, assigned as "B" in the overall SCORAD calculation).
 
Subjective assessment of itch and of sleeplessness is recorded for each symptom by the patient or relative on a VAS, where 0 is no itch (or sleeplessness) and 10 is the worst imaginable itch (or sleeplessness), with a maximum possible score of 20 (caring d or "C" in the anorn!
 
	
 
Change from baseline in SCORAD score
 
Percent change from baseline in SCORAD score
 
SCORAD75
 
SCORAD90
 
	Change from baseline: observed SCORAD score – baseline SCORAD score % change from baseline: 100 × Observed score – Baseline 8aseline % Improvement in SCORAD from baseline ≥75%: % change from baseline ≤-75 % Improvement in SCORAD from baseline ≥90%: % change from baseline ≤-90	assessments performed by subject cannot be saved. Missing if baseline or observed value is missing. Missing if baseline or observed value is missing. Missing if baseline or observed value is missing.
	(assigned as "C" in the overall SCORAD calculation.			
Modified Total Lesion Symptom Scale	The Modified Total Lesion Symptom Scale is an investigator-reported scale that combines the evaluation of hand eczema (HE) lesion severity (erythema, edema, desquamation, fissures, hyperkeratosis or lichenification, and vesicles) with the intensity of pruritus	Percent change from baseline in mTLSS	This composite score assigns 0 (mild) to 3 (severe) to each component, giving a maximum disease severity of 21. The recall period for this scale is the present time.	If 1 question in a domain is missing, that domain is missing.

	or pain to assess the severity of symptoms.			
Pruritis Numeric Rating Scale (NRS)	The Pruritus Numeric Rating Scale (NRS) is a participant-reported, single- item, daily, 11-point scale.	Percent change from baseline Pruritis NRS Score 4-point improvement in Pruritis NRS Score 3-point improvement in Pruritus NRS Score	The Pruritus NRS is used by participants to rate their worst itch severity over the past 24 hours with 0 indicating "No itch" and 10 indicating "Worst itch imaginable." Assessments will be recorded daily by the participant. The minimal clinically important change is 3 points. Participants will record the pruritus assessments daily using an electronic diary at home. As indicated in the SoA (Section 1.3), initial electronic diary entries for Pruritus NRS should be completed a minimum of 4 of 7 days before baseline.	Baseline weekly mean score is missing if the patient has 3 or fewer responses within the week before baseline. Post-baseline weekly mean score is missing if the patient has no responses within the week.
Skin Pain Numeric Rating Scale (NRS)	The Skin Pain NRS is a participant- reported, 11-point horizontal scale anchored at 0 and 10, with 0 representing "no pain" and 10 representing "worst pain imaginable."	Percent change from baseline in Skin Pain NRS Score 4-point improvement in Skin Pain NRS Score	Overall severity of a participant's skin pain is indicated by selecting the number that best describes the worst level of skin pain in the past 24 hours. Assessment will be recorded daily by the participant.	Baseline weekly mean score is missing if the patient has 3 or fewer responses within the week before baseline. Post-baseline weekly mean score is missing if the patient has no responses within the week.
Sleep-Loss Scale	The Sleep-Loss Scale is a participant- reported, single-item, daily scale that measures the extent of sleep loss due to interference of itch over the last night.	Percent change from baseline in Sleep Loss Score 2-point improvement in Sleep Loss Score	The Sleep-Loss Scale is rated based on a 5-point Likert scale (0 [not at all] to 4 [unable to sleep at all]). Assessment will be recorded daily by the participant. The minimal clinically important change is 3 points.	Baseline weekly mean score is missing if the patient has 3 or fewer responses within the week before baseline. Post-baseline weekly mean score is missing if the patient has no responses within the week.

Atopic Dermatitis Control Tool	The Atopic Dermatitis Control Tool is a patient-reported, simple, brief tool for adults and adolescents that evaluates 6 symptoms and effects associated with AD over the past week	Percent change from baseline in ADCT Total Score	Each of the 6 Atopic Dermatitis Control Tool items has a score range from 0 (no problem) to 4 (worst), rating the severity of each concept; the total score ranges from 0 to 24, which is the summation of the responses to all the items. A score of ≥7 points was derived as the threshold to identify participants "not in control." The threshold for meaningful within-person change was estimated to be 5 points.	If 1 question in a domain is missing, that domain is missing.
Participant Reported Satisfaction Question	The question on participant satisfaction asks "How satisfied are you with this treatment's ability to treat your skin condition?"	PRSQ Score	The response options range from 1 (not satisfied) to 5 (completely satisfied).	Single item, missing if missing.
WPAI-AD	The Work Productivity and Activity Impairment Questionnaire–Atopic Dermatitis is a participant-reported, 6- item questionnaire that records impairment due to AD over the past 7 days in adolescents and adults	Percent change from baseline in WPAI AD Absenteeism Score Percent change from baseline in WPAI AD Presenteeism Score Percent change from baseline in WPAI AD Work Productivity Loss Score Percent change from baseline in WPAI AD Activity Impairment Score	The Work Productivity and Activity Impairment Questionnaire– Atopic Dermatitis consists of 6 items grouped into 4 domains: absenteeism (work time missed), presenteeism (impairment at work or reduced on the job effectiveness), work productivity loss (overall work impairment or absenteeism plus presenteeism), and activity impairment. Absenteeism, presentism, and work productivity will only be reported by those who are currently employed (working for pay) at the time of the scale completion. The recall period for the scale is over the past 7 days. Scores are calculated as impairment percentages (Reilly et al. 1993), with higher scores indicating greater	If 1 question in a domain is missing, that domain is missing.

## J2T-MC-KGBO (Lebrikizumab) Statistical Analysis Plan Version 2

	impairment and less productivity	

Abbreviations: AD = atopic dermatitis; HRQoL = health-related quality of life; NA = not applicable; QoL = quality of life. a Secondary endpoints.

